
Statistical Assumptions
	
 • 10% attack rate for close contacts (or 10% progression of disease to hospitalization among those symptomatic at entry) • Comparison of Proportions by Fisher’s Exact test for disease incidence; • Comparison of ordinal scale of disease severity by proportional odds model • N=621 sample per arm has 90% power to detect a 50% relative risk reduction (i.e. $\leq 5.0\%$) in disease incidence or 50% decrease in the ordinal disease severity (to $\leq 4.25\%$ disease incidence and $\leq 1\%$ hospitalization). • 20% dropouts, inflates sample size to n=750 per arm

Schematic of Study Design:

If hospitalization occurs, this SAE will be followed for up to 90 days

For participants who develop symptomatic disease, they will be followed for up to 90 days to assess final outcome status in the event of hospitalization.

Stratification is based on symptom status at baseline

1. 1500 asymptomatic healthcare workers or household contacts exposed to COVID-19
2. 1500 symptomatic COVID-19 outpatients

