11.2 Sample Size Considerations

Two cohorts of 1500 subjects each:

- 1) Asymptomatic persons exposed to COVID-19 disease (750 in placebo, 750 in intervention);
- 2) Symptomatic outpatient COVID-19 disease (750 in placebo, 750 in intervention).

Assuming 90% power, a two-sided alpha = 0.05 and loss to follow-up up to 20%, for each cohort the planned sample size is 750 participants per arm based on the following assumptions:

- 10% transmission rate from COVID-19 cases to close contacts
- For those with symptomatic illness the proportions at day 14 in the placebo group are 90%, 8% and 2%, respectively for illness without hospitalization, hospitalization with ICU stay or death, and hospitalization with an ICU stay or death.

The estimated transmission rates are uncertain. Table 1 below (for the asymptomatic cohort with exposure) shows that we are well powered to detect even a smaller (40%) relative reduction in the incidence of COVID 19 with 80% power for transmission rates of at least 10% with placebo. Table 2 (for the symptomatic group) shows that we are well powered to detect a common odds ratio of 0.6-0.75 under the assumption that the control proportions for illness without hospitalization, hospitalization without ICU stay or death and hospitalization with ICU stay or death are 90%, 8% and 2%, respectively.

Table 1. Sample Size Table for Asymptomatic Participants (Healthcare worker or household contact) With Exposure

Estimated transmission rate with placebo	Estimated transmission rate with drug	Percent relative reduction in transmission rate	Sample size (per arm) with 90% power	Sample size (per arm) with 80% power
10%	5%	50%	621	474
	6%	40%	1014	771
12%	6%	50%	509	389
	7.2%	40%	831	632
15%	7.5%	50%	398	304
	9%	40%	648	493

Table 2. Sample size table for participants with symptomatic disease, assuming that the control proportions are 90% illness with no hospitalization, 8% hospitalization with no ICU stay or death and 2% hospitalization with ICU stay or death.

Log Odds Ratio	Odds Ratio	Sample size (per group) with 90% power	Sample size (per group) with 80% power
0.60	1.82	805	601
0.65	1.91	697	521
0.70	2.01	610	456
0.75	2.12	539	403

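### Section 11.2 reports Table 2's log odds ratios (0.60 to 0.75) as odds ratios; at a true odds ratio of 0.75 the symptomatic cohort has about 30% power

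*Combined protocol and SAP*

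**What the plan says.** Section 11.2 plans 750 participants per arm in the symptomatic cohort. The design settings are "Assuming 90% power, a two-sided alpha = 0.05 and loss to follow-up up to 20" percent. The sizing uses a three-level ordinal scale at day 14, and the Table 2 caption gives "control proportions are 90% illness with no hospitalization, 8% hospitalization with no ICU stay or death and 2% hospitalization with ICU stay or death".

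The text above the tables says that Table 2 shows the cohort is "well powered to detect a common odds ratio of 0.6-0.75 under the assumption that the control proportions" are as just given.

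The first column of Table 2 is headed "Log Odds Ratio" and runs 0.60, 0.65, 0.70, 0.75. The next column gives odds ratios of 1.82, 1.91, 2.01 and 2.12. The first row, for example, reads "0.60 1.82 805 601": log odds ratio, odds ratio, number per group for 90% power, number per group for 80% power.

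The Summary (Statistical Assumptions) states the target for this cohort as a "50% decrease in the ordinal disease severity", with 4.25% and 1% or less in the two worse categories, from 621 per arm at 90% power. It adds "20% dropouts, inflates sample size to n=750 per arm".

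**The concern.** The sentence cites Table 2 for a range of odds ratios that the table does not contain. An odds ratio of 0.75 is a log odds ratio of 0.29 in absolute value, less than half the smallest effect tabulated (0.60).

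The error makes the design look much more sensitive than it is. A reader of section 11.2 would conclude that a 25% to 40% reduction in the odds of a worse outcome is within reach, whereas the cohort was sized for roughly a halving. A null result on the ordinal scale could then be taken as evidence against moderate effects that the trial had little chance of detecting.

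The protocol also ends up with two incompatible target effects for one cohort: about 0.5 in the Summary and 0.6 to 0.75 in section 11.2. Section 11.3 has the DSMB receive conditional power for both cohorts under the study design parameters, so those parameters need to be unambiguous.

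**Working it through.** **Inputs.** Two-sided alpha 0.05; power 90% and 80%; control proportions 0.90 / 0.08 / 0.02; 750 per arm (all from section 11.2). A 20% loss leaves 750 × 0.80 = 600 evaluable per arm. The analysis model is proportional odds (Summary and section 11.4).

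**Formula.** Whitehead's sample size for the proportional odds model with 1:1 allocation:

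n per group = 6 (z₀.₉₇₅ + z_power)² / [(log OR)² × K], where K = 1 − Σ p̄ᵢ³ and p̄ᵢ is the mean of the two arms' proportions in category i.

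The squared z-sum is 10.507 for 90% power and 7.849 for 80%. Treatment proportions come from multiplying the control cumulative odds (0.90/0.10 = 9 and 0.98/0.02 = 49) by exp(|log OR|), the direction of benefit.

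**Step 1: reproduce Table 2, taking 0.60 to 0.75 as log odds ratios.** For 0.60, the treatment proportions are 94.25 / 4.64 / 1.11%, the means are 0.9213 / 0.0632 / 0.0155, and K = 0.2178. Then n = 6 × 10.507 / (0.36 × 0.2178) = 803.9 for 90% power and 6 × 7.849 / (0.36 × 0.2178) = 600.5 for 80%.

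| Log OR | OR | 1/OR | n (90%), computed | Table 2 | n (80%), computed | Table 2 |
|---|---|---|---|---|---|---|
| 0.60 | 1.82 | 0.55 | 803.9 | 805 | 600.5 | 601 |
| 0.65 | 1.92 | 0.52 | 695.7 | 697 | 519.7 | 521 |
| 0.70 | 2.01 | 0.50 | 609.0 | 610 | 454.9 | 456 |
| 0.75 | 2.12 | 0.47 | 538.4 | 539 | 402.2 | 403 |

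Every entry agrees within 2. (The table's 1.91 is exp(0.65) = 1.9155 truncated, which is immaterial.) One-sided alpha does not reproduce the first row (656 / 474), nor does a shift in the direction of harm (501 / 375). The table is therefore correct, and its first column is on the log scale as headed.

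**Step 2: the same formula, taking 0.6 to 0.75 as odds ratios, as the sentence says.** Power = Φ(|log OR| × √(nK/6) − 1.960). For OR 0.75, |log OR| = 0.2877, the treatment proportions are 92.31 / 6.18 / 1.51%, and K = 0.2422.

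- n for 90% power = 63.045 / (0.0828 × 0.2422) ≈ 3,145.
- Power with 600 per arm = Φ(1.416 − 1.960) = 0.293.
- Power with 750 per arm = Φ(1.583 − 1.960) = 0.353.

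| OR | n per arm, 90% | n per arm, 80% | Power, 600 per arm | Power, 750 per arm (no loss) |
|---|---|---|---|---|
| 0.60 | 1,078 | 805 | 68% | 77% |
| 0.65 | 1,476 | 1,102 | 54% | 64% |
| 0.70 | 2,098 | 1,567 | 41% | 49% |
| 0.75 | 3,145 | 2,350 | 29% | 35% |

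The 805 at OR 0.60 and 80% power matches Table 2's 805 at log OR 0.60 and 90% power only by coincidence.

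**Step 3: cross-checks.** A simulation of the tie-corrected Wilcoxon test (40,000 replicates) gives power of 0.288 (600 per arm) and 0.350 (750) at OR 0.75, and 0.666 and 0.763 at OR 0.60. Using 621 per arm, the Summary's figure before inflation, gives 30% at OR 0.75.

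**Step 4: what the design can detect.** Solving the formula at 600 per arm gives 80% power at |log OR| = 0.60 (OR 0.55) and 90% power at |log OR| = 0.71 (OR 0.49).

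**Step 5: which effect was intended.** A common odds ratio of 0.50 applied to 90 / 8 / 2% gives 94.7 / 4.25 / 1.01% and needs 620 per arm for 90% power. That matches the Summary's 4.25%, 1% and 621. An odds ratio of 0.75 gives 6.2% and 1.5%, which does not match.

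**The case against.** The strongest reply is that one word, log, has been dropped. No sample size was computed from an odds ratio of 0.6 to 0.75, Table 2 is correct and correctly headed, and the Summary states the intended effect properly. All of that is true: the Summary contradicts the misstatement and does not repeat it. It shows what was meant, but it does not make the sentence in section 11.2 right.

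The second point is that the ordinal scale is now secondary in this cohort. The primary endpoint is the change in the visual analog symptom score (sections 3.2.1 and 11.4), so no primary test or boundary depends on the sentence. This also stands and limits the reach of the error. However, section 11.2 gives no other justification for 750 per arm in the symptomatic cohort, and the second hypothesis in section 11.1 concerns progression to hospitalization or death, which is what the scale measures.

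Third, the sentence names no power level, and the sentence before it uses 80%. With log restored, the claim holds at 80%: the weakest row needs 601 against 600 evaluable. It does not hold at the 90% stated at the head of section 11.2. That row needs 805, more than the 750 randomized, and with 600 evaluable only the 0.75 row (539) reaches 90%.

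Finally, 0.75 is the worst end of the claimed range. At the best end, 0.60, power is 68% to 77%, closer to adequate but still below 80% even with no loss.

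**Conclusion.** The concern holds. Section 11.2 presents log odds ratios as odds ratios and so claims good power for effects the cohort cannot reliably detect. At a true common odds ratio of 0.75, power is about 30% after the planned loss (29% with 600 per arm, 30% with 621) and 35% with none. No odds ratio from 0.60 to 0.75 reaches 80%. The effects Table 2 actually covers are odds ratios of 0.55 to 0.47.

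These figures rest on the protocol's own control proportions, two-sided alpha 0.05, proportional odds and benefit in the treated arm. The error is confined to one sentence and to an endpoint that is now secondary. Table 2 and the planned sample size computed from it are unaffected.

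**What to change.** Delete the statement about an odds ratio of 0.6 to 0.75. In its place, state that with 600 evaluable per arm the ordinal comparison has 80% power for a common odds ratio of about 0.55 (absolute log odds ratio 0.60) and 90% power for about 0.49 (0.71). The second figure comes from the formula and should not be attributed to Table 2, which has no 0.71 row. If only the wording is corrected, it should read as a log odds ratio of 0.60 to 0.75, equivalent to an odds ratio of 0.55 to 0.47, with 80% power after 20% loss.

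Add the reciprocal odds ratios (0.55, 0.52, 0.50, 0.47) to Table 2 so that the text, the table and the Summary's 50% target can be compared directly. State in section 11.2 that the ordinal scale is now secondary.

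The cost is a text edit. The design, sample size and analyses do not change, but the stated detectable effect becomes less favourable.

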11.3 Planned Interim Analyses

A Lan-DeMets spending function analog of the O'Brien-Fleming boundaries will be provided at each DSMB report for the primary outcome for each cohort. The O'Brien-Fleming boundaries will be truncated at $\alpha = 0.001$ ($|Z| > 3.09$). For each cohort, interim analyses are separately planned at 25%, 50% and 75% of trial enrollment.

As enrollment may be brisk, the timing of interim analyses may be altered at PI discretion based on that pace of enrollment. It may be possible that the trial is fully enrolled by the time day 14 outcomes are available for the first 25% enrolled. In this case, any further analyses would be related as to when to release interim results.

At the first DSMB review, the stopping boundary is unlikely to be crossed. The purpose of this early review will assess the trends for safety/efficacy and allow for the DSMB to determine the probable timing of further reviews based on the pace of enrollment.

Should a stopping boundary be crossed, we would recommend an analysis to determine whether the findings are consistent across secondary endpoints, such that a clear answer is achieved. Starting with the 2nd DSMB review (at approximately 50% enrollment) the DSMB will be given the conditional power for both cohorts under both the study design parameters and the current data. If the conditional power is less than 20% then trial discontinuation may be considered.

In the event of early halting due to efficacy of the intervention, the study will immediately convert to an open label observational cohort of hydroxychloroquine prescribed to all consented participants in the relevant cohort.

In the event of early halting due to futility of no effect, a protocol modification will be made to alter the intervention.

Based on the public health situation, the DSMB has the prerogative to alter the stopping rules.

Sample Size Re-estimation:

At time of ~50% enrollment, a sample size re-estimation should occur based on the disease transmission rate in the control group. The *a priori* assumption (based on limited data) is 10% transmission risk. The new sample size estimation will take into account the updated transmission rate with no treatment and will be powered to detect a 50% relative reduction in outcome.

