FWA	Federalwide Assurance
GCP	Good Clinical Practice
HIPAA	Health Insurance Portability and Accountability Act
ICF	Informed Consent Form
ICH	International Conference on Harmonisation
IDS	Investigational Drug Services
IEC	Independent or Institutional Ethics Committee
IND	Investigational New Drug Application
IRB	Institutional Review Board
MERS-CoV	Middle East respiratory syndrome coronavirus
MOP	Manual of Procedures
N	Number (typically refers to subjects)
NIAID	National Institute of Allergy and Infectious Diseases, NIH
NIH	National Institutes of Health
OCRA	Office of Clinical Research Affairs, DMID, NIAID, NIH, DHHS
OHRP	Office for Human Research Protections
OHSR	Office for Human Subjects Research
ORA	Office of Regulatory Affairs, DMID, NIAID, NIH, DHHS
PCR	Polymerase chain reaction
PHI	Protected Health Information
PI	Principal Investigator
SAE	Serious Adverse Event
SOP	Standard Operating Procedure
US	United States
WHO	World Health Organization

[figure not shown]
Summary

Full Title:	Post-exposure prophylaxis or Preemptive Therapy for coronavirus: A Pragmatic Randomized Clinical Trial
Short Title:	COVID-19 PEP RCT
Clinical Phase:	III
Sponsor:	Investigator-Initiated Protocol, University of Minnesota
Principal Investigator:	[name] MPH
Accrual Ceiling	3000
Study Population	
 • Adult Household contacts or Healthcare workers exposed to persons with COVID-19 disease within 4 days (n=1500), or • Non-hospitalized adults with symptomatic COVID-19 disease within 4 days of onset (n=1500)
Objective	
 1) Test if hydroxychloroquine can prevent development of COVID-19 disease after known exposure to the SARS-CoV2 virus. 2) Test if early preemptive therapy in non-hospitalized adults with symptomatic COVID-19 disease can prevent disease progression and hospitalization
Study Design	
Double-blind, randomized placebo-controlled clinical trial Internet-based trial driven by self-report. Study medicine delivered by FedEx to consented participants. Follow up through 14 days, with SAEs followed up to 90 days

Intervention Arm:	Hydroxychloroquine 200mg tablet.

	
800 mg orally once, followed in 6 to 8 hours by 600 mg, then 600 mg once a day for 4 consecutive days (5 days in total)
 
(This is a modified malaria dosing for hydroxychloroquine)

Control Arm:	
Placebo 4 tabs once, followed in 6 to 8 hours by 3 tabs, then 3 tabs once a day for 4 consecutive days (5 days in total)

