3.2.2 Secondary Outcome Measures

- Incidence of hospitalization or death
- Incidence of confirmed SARS-CoV-2 detection
- Incidence of symptoms compatible with COVID-19 (possible disease)
- Incidence of all-cause study medicine discontinuation or withdrawal
- Incidence of adverse reactions
- Symptom severity on day 5 or 14 via visual analog scale
- Ordinal Scale of COVID-19 Disease Severity at day 14 (among those who are symptomatic at trial entry)
 - Illness without hospitalization
 - Hospitalization (or post-hospital discharge)
 - Hospitalization with ICU stay or Death

Assessment of outcome measures will be primarily by self-report. As necessary, COVID19 disease will be verified from public health records, medical records, or death certificates. The primary endpoints are different for the two cohorts (those who are asymptomatic with known exposure; or those who are symptomatic at trial entry), and analyses will be done separately for the two cohorts.

The primary analysis will use PCR+ confirmed disease. However if the absence of sufficient testing supplies continues then outpatients will not be offered SARS-CoV-2 testing unless they are sick enough to be hospitalized. In that case an alternate a priori planned analysis will define incident COVID19 disease as a composite of SARS-CoV-2 PCR+ confirmed result OR symptomatic disease (i.e. possible) COVID-19 in those without testing.

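### Section 11.3 re-estimates sample size from the control rate at a fixed 50% reduction, with no floor and no named endpoint, so under the symptom composite non-COVID illness would lower N when N should rise

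*Combined protocol and SAP*

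**What the plan says.** Protocol section 11.3, under Sample Size Re-estimation, states that at roughly 50% enrolment "a sample size re-estimation should occur based on the disease transmission rate in the control group". The design value is 10%. The updated control rate replaces it, and the new size "will be powered to detect a 50% relative reduction in outcome". The paragraph gives no minimum size, does not say whether N may fall, and does not identify the endpoint definition behind the control rate. The SAP contains no re-estimation rule. Because the rule is expressed through a transmission rate, I read it as applying to the asymptomatic cohort.

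The original size is in section 11.2 and the Summary. It assumes "10% transmission rate from COVID-19 cases to close contacts", and "N=621 sample per arm has 90% power to detect a 50% relative risk reduction". Enrolment is set at 1,500 per cohort ("750 in placebo, 750 in intervention"), with up to 20% loss to follow-up. The Summary lists an "Accrual Ceiling" of 3000, which the two cohorts of 1,500 use in full.

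Section 3.2.2, repeated at the head of the SAP, makes PCR-confirmed disease the primary definition. If the testing shortage persists, it substitutes a composite of a positive PCR or "symptomatic disease (i.e. possible) COVID-19 in those without testing". The rationale in section 5.2 records that testing was already limited in many places on 20 March 2020, so the composite is a realistic prospect.

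**The concern.** A higher control rate can have two causes, and they call for opposite responses. If more participants develop COVID-19 and the drug halves that risk, the 50% reduction still holds and fewer participants are needed. If more participants have other illnesses that are counted as possible COVID-19, the drug prevents none of the extra events. The relative reduction then falls below 50% and more participants are needed.

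The rule sees only the control rate and treats both causes as the first. Under the composite it can therefore shorten the asymptomatic cohort on the strength of events that dilute its primary comparison. The risk is that a real effect on COVID-19 is reported as no effect, after a mid-course cut that appeared to preserve 90% power.

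**Working it through.** **Inputs from the documents.** Two-sided alpha 0.05, 90% power, 1:1 allocation, control rate 10%, 50% reduction, 621 evaluable per arm, 750 enrolled per arm, 20% loss (section 11.2 and Summary), and Fisher's exact test (section 11.4). Planned evaluable number: 750 × 0.80 = 600 per arm.

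**Assumptions, not in the documents.** True COVID-19 is 10% on placebo and 5% on drug. Non-COVID illness counted as an event occurs with probability b, is equal in both arms, is independent of COVID-19 and is unaffected by the drug. The documents give no value for b, so 2%, 5% and 8% are shown.

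**1. Reproduce the plan's figure.** With d = p1 − p2 and p̄ their mean:

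- n0 = [1.960 √(2p̄(1−p̄)) + 1.282 √(p1(1−p1) + p2(1−p2))]² / d²
- n = (n0/4) [1 + √(1 + 4/(n0 d))]² (continuity correction)

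For 10% vs 5%, n0 = 581.1 and n = 620.4, which rounds up to 621 as stated. All 12 cells of Table 1 reproduce in this way. At a 50% reduction and 90% power, the table falls from 621 (10%) to 509 (12%) to 398 (15%). That is the direction in which the rule moves N when the control rate rises.

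**2. Apply the rule to composite rates.** Control rate = 1 − 0.90(1−b); drug rate = 1 − 0.95(1−b). For b = 5%:

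- control 1 − 0.90 × 0.95 = 14.5%; drug 1 − 0.95 × 0.95 = 9.75%
- true relative reduction 1 − 9.75/14.5 = 32.8%
- the rule assumes 14.5% vs 7.25%: n0 = 385.4, n = 412.6, so 413 per arm
- 90% power against 14.5% vs 9.75% needs 1,032 per arm

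**3. Power, by exact enumeration of the two-sided Fisher test** (no adjustment for interim looks). With no background illness, 600 per arm gives 89.7%.

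| b | Control vs drug | True reduction | N from rule | Power at rule N | Power at 600 | N needed for 90% |
|---|---|---|---|---|---|---|
| 2% | 11.8% vs 6.9% | 41.5% | 519 | 74.9% | 81.1% | 781 |
| 5% | 14.5% vs 9.75% | 32.8% | 413 | 51.5% | 68.6% | 1,032 |
| 8% | 17.2% vs 12.6% | 26.7% | 341 | 35.5% | 58.0% | 1,301 |

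**4. Split the loss.** The cost of dilution with N held at 600 is 89.7 minus the power at 600: 8.6, 21.1 and 31.7 points. The further cost of the rule is the power at 600 minus the power at the rule's N: about 6, 17 and 22 points.

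**5. Allow for testing.** Only untested participants can contribute symptom-only events, so the table is an upper case. Scaling b by the untested share:

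| Case | N from rule | Power at rule N | Power at 600 |
|---|---|---|---|
| b = 2%, half untested | 566 | 83.1% | 85.4% |
| b = 5%, half untested | 498 | 70.5% | 78.9% |
| b = 2%, one quarter untested | 592 | 87.1% | 87.6% |

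The rule's own cost in these cases is about 1 to 8 points.

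**The case against.** **The text never says that N will be cut.** This is true. A reader might infer that section 11.3 commits the trial to shrinking. It says only that a re-estimation should take place. A reduction follows from the formula when no floor is stated; it is not an announced decision.

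**The rule may be right.** It is, if confirmed disease supplies the rate or if the whole rise is true COVID-19: 398 per arm gives 90% power at 15% vs 7.5%. The defect is conditional on the composite, and the text does not settle that condition.

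**Most of the lost power is not the rule's doing.** This stands. A reader might attribute the whole fall from 90% to 51% at b = 5% to the re-estimation, but dilution by the composite costs more than the rule in every row.

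**Chance alone could cut N.** This adds little. With a true 10% rate and 375 × 0.80 = 300 evaluable controls at half-way, the rule returns fewer than 600 per arm in 45% of trials and fewer than 500 in 11%. It also returns more than 621 in 47% and more than 750 in 19%. Such sampling error affects any re-estimation of this kind, and 500 per arm still gives 83% power for 10% vs 5%.

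**The practical scope is limited.** This is partly right. Section 11.3 warns that enrolment may finish before early outcomes are available. About 375 per arm are already enrolled at the look. From the second review the DSMB also sees conditional power under both the design and the current data, so a diluted effect would not be wholly hidden. But 413 evaluable is 413/0.8, or about 517 enrolled, so a cut would still be possible at b = 5%. The SAP clarification that keeps missing outcomes in the denominator would, if applied here, lower the observed rate and push N up.

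**N could still rise.** It could, by amending the ceiling. The documents do not support saying that an increase is ruled out, only that the two cohorts leave no unallocated room.

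**Conclusion.** The point holds in conditional form. As written, the rule updates one quantity, fixes the other at 50%, sets no floor and names no endpoint. If the composite supplies the control rate and contains any non-COVID illness that the drug does not prevent, the rule moves N the wrong way. That direction does not depend on the value of b.

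The size does. With b applied to everyone, the rule costs about 6 points of power at 2%, 17 at 5% and 22 at 8%, beyond the loss due to the composite itself. With half or fewer untested, the cases checked give about 1 to 8 points. All of these assume true COVID-19 of 10% vs 5% and background rates that the documents do not supply.

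This is a gap to close before the re-estimation is run. It does not show that the trial will be cut or that its 90% power is already lost. Allowing a decrease is not an error in itself; the fault is allowing one on a rate whose composition is unspecified. It should be fixed, but it is not a fatal flaw.

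**What to change.** In section 11.3:

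1. State that the re-estimation may not reduce enrolment below the planned 750 per arm.
2. Name the endpoint definition, PCR-confirmed or composite, that supplies the control rate.
3. If the composite governs, apply the 50% reduction only to the COVID-19 part and enter an explicit background rate for unconfirmed illness. With COVID-19 rate p and background b, the target becomes 1 − (1−p)(1−b) vs 1 − (1−p/2)(1−b).
4. If the resulting N does not fit within the 3,000 ceiling, either amend the ceiling or restate the power that can be achieved.

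The floor alone does not restore 90% power under dilution: at b = 5%, 750 enrolled (600 evaluable) gives 69%. It only stops the rule from deepening the loss, which is why items 3 and 4 are needed.

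The cost is protocol wording. The downside is that the cohort may keep its planned 1,500 when a pure calculation would have allowed fewer. No participants are added beyond the current plan unless the ceiling is amended.
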